### **11.4 Early Withdrawal from Treatment**

If a subject withdraws or is withdrawn prior to the last scheduled visit, all efforts should be made to perform the end of study assessments (as per Visit 4). Additional follow-up by telephone may be required to obtain information regarding follow-up of AEs (both non-serious and serious) ongoing at the time of study discontinuation.

The date the subject withdraws/is withdrawn from the study and the reason(s) for discontinuation will be recorded on the subject's eCRF.

### ***11.5 Criteria for Withdrawal of Study Treatment***

Subjects may withdraw from the study at any time without stating a reason and without prejudice to further treatment. The investigator may withdraw a subject from the study and discontinue study treatment and assessments at any time. Events that will result in discontinuation of treatment include:

1. Inability to tolerate Chronocort® secondary to perceived or observed side effects
2. Pregnancy (not due to safety reasons but because pregnancy may interfere with the primary endpoint)
3. Any other changes to clinical signs or changes in laboratory values, physical status or AEs that could compromise the subject's status if they were to continue with the study or if the investigator feels that it is not in the best interests of the subject

The sponsor reserves the right to request the withdrawal of a subject due to protocol violation, administrative or other reasons, or in the event of emergence of adverse risk data on the product.

If a subject withdraws from the study prior to study completion, the reason for withdrawal should be sought and recorded on the eCRF. AEs should be followed up until resolution.

If a subject withdraws from the study they will not be eligible to participate in the extension study.

### ***11.6 Replacement of Withdrawn Subjects***

120 subjects will be randomised to account for withdrawals anticipated during the course of the study and to provide 102 evaluable subjects.

### ***11.7 Additional Information for the Study Population***

Females presenting with oligomenorrhoea or amenorrhoea who are aged  $\leq 55$  years of age should be considered potentially fertile and therefore, as well as undergoing pregnancy testing like all other female subjects, will be expected to be using an acceptable method of contraception as noted below.

Acceptable forms of contraception include:

1. Established use of oral, injected or implanted hormonal methods of contraception (including oestrogen-containing products) – note that use of these methods of contraception must remain the same throughout the study in both nature and dose. The type of contraception should have been ongoing for  $\geq 90$  days prior to the study and at least 7 days after the final dose. If  $< 90$  days prior to the study, additional use of a double barrier method until 90 days is reached is required.
2. Placement of an intrauterine device (IUD) or intrauterine system (IUS).
3. Barrier methods of contraception: condom or occlusive cap (diaphragm or cervical/vault caps) with spermicidal foam/gel/film/cream/suppository. The following should be noted:
  - Failure rates indicate that, when used alone, the diaphragm and condom are **not** highly effective forms of contraception. Therefore the use of additional spermicides does confer additional theoretical contraceptive protection.
  - However, spermicides alone are inefficient at preventing pregnancy when the whole ejaculate is spilled. **Therefore, spermicides are not a barrier method of contraception and should not be used alone.**

4. Male sterilisation (with the appropriate post-vasectomy documentation of the absence of sperm in the ejaculate). [For female subjects on the study, the vasectomised male partner should be the sole partner for that subject].
5. True abstinence: When this is in line with the preferred and usual lifestyle of the subject. Periodic abstinence, such as calendar, ovulation, symptothermal, post ovulation methods, and withdrawal are not acceptable methods of contraception

### ***11.8 Completion of the Study***

The study will be completed when all subjects have completed the last visit or telephone call of this study.

### ***11.9 Subject Payment Schedule***

Reasonable subject travel costs will be reimbursed. Where appropriate, costs for overnight accommodation prior to clinic admittance will be reimbursed, and in some cases a compensation or inconvenience payment may be made to subjects.

### ***11.10 Overdose***

In the event of an overdose, the subject should immediately contact the Investigator or Study Nurse for advice. There is no antidote available for Chronocort®.

## **12 Adverse Events and Toxicity Management**

### ***12.1 Adverse Event Definition***

An AE is defined as (21CFR312.32): “Any untoward medical occurrence associated with the use of a drug in humans, whether or not considered drug related.” An AE can therefore be any unfavourable and unintended sign (including an abnormal laboratory finding), symptom, or disease temporally associated with the use of a medicinal (investigational) product, whether or not related to the medicinal (investigational) product. This includes any newly occurring event or previous condition that has increased in severity or frequency since the administration of study drug.

### ***12.2 Adverse Event Collection***

AEs will be collected for all subjects from the time of consent up to phone call T4 (30 days ± 3 days) following the last visit or, if applicable, the Early Withdrawal visit. Any ongoing AEs post study will be followed to resolution or stabilisation if resolution is not expected. Only treatment emergent AEs will be included in the main safety analysis: other AEs will be listed.

Details of any AEs, signs, and symptoms will be collected, including details of onset, resolution, frequency, severity, seriousness, relationship to the drug, effect on the study drug, treatments administered, and outcome. All AEs will be followed, whenever possible, until it returns to the baseline condition or becomes stable with no further change expected. In the event of any abnormalities considered to be clinically significant by the investigating physician, subjects will be followed up with appropriate medical management until values are considered to be clinically acceptable. Referral or collaborative care will be organised if required.

### **12.3 Reporting of Adverse Events**

Individual AEs should be evaluated by the investigator and recorded in the eCRF. AEs must be reported equally for both study treatments, regardless of whether the investigator thinks the AEs are related to the study treatment.

#### **12.3.1 Diagnoses vs. signs/symptoms**

Each AE should be recorded to represent a single diagnosis. Accompanying signs (including abnormal laboratory values if not constituting AEs themselves or ECG findings) or symptoms should NOT be recorded as additional AEs. If a diagnosis is unknown, sign(s) or symptom(s) should be recorded as the AE(s).

#### **12.3.2 Laboratory values**

Changes in laboratory values may be considered AEs if they are judged to be clinically significant (i.e., if some action or intervention is required or if the investigator judges the change to be beyond the range of normal physiological fluctuation). If abnormal laboratory values are the result of pathology for which there is an overall diagnosis (e.g., increased creatinine in renal failure), the diagnosis only should be reported as an AE.

#### **12.3.3 Pre-existing conditions**

Pre-existing conditions (present before the start of the AE collection period) are considered concurrent medical conditions and should NOT be recorded as AEs. However, if the subject experiences a worsening or complication of such a concurrent condition, the worsening or complication should be recorded as an AE. Investigators should ensure that the AE term recorded captures the change in the condition (e.g., “worsening of...”).

#### **12.3.4 Pre-planned surgeries or procedures**

Pre-planned procedures (surgeries or therapies) that were scheduled prior to the start of AE event collection are not considered AEs. However, if a pre-planned procedure is performed early (e.g., as an emergency) due to a worsening of the pre-existing condition, the worsening of the condition should be captured as an AE.

#### **12.3.5 Insufficient clinical response (lack of efficacy)**

Insufficient clinical response, efficacy, or pharmacological action, should NOT be recorded as an AE. The investigator must make the distinction between exacerbation of pre-existing illness and lack of therapeutic efficacy.

#### **12.3.6 Overdose**

Cases of drug overdose without manifested side effects are NOT considered AEs.

### **12.4 Assessment of Adverse Event Severity**

The following guidelines for rating severity of AEs should be used:

#### **Mild:**

Awareness of signs or symptoms, but easily tolerated; are of minor irritant type; no loss of time from normal activities; symptoms would not require medication or a medical evaluation; signs and symptoms may be transient, disappearing during continued treatment with study medication.

Moderate:

Discomfort enough to cause interference with usual activities; the study medication may have been interrupted.

Severe:

Incapacitating with inability to do work or do usual activities; signs and symptoms may be of systemic nature or require medical evaluation; the study drug may have been stopped, and treatment for the event may be required.

The term “severe” is often used to describe the intensity of a specific event, as in mild, moderate, or severe myocardial infarction; the event itself, however, may be of relatively minor medical significance, such as severe headache. This is not the same as serious, which is based on subject/event outcome or action criteria usually associated with events that pose a threat to a subject’s life or functioning.

### *12.5 Assessment of Adverse Event Causality/Relatedness*

All AEs will be assigned one of the following assessments of causality (note that both Chronocort® and the standard glucocorticoid replacement therapy used in the comparator arm are considered IMPs in this study):

- Not related
- Related to the IMP
- Related to sick day medication
- Related to an interaction between IMP and sick day medication
- Related to either IMP or sick day medication

All AEs judged by either the investigator or the sponsor as having a reasonable suspected causal relationship to an IMP, or are due to an interaction with an IMP, qualify as adverse drug reactions (ADRs).

Appendix 3 provides a comprehensive list of events that are anticipated to occur in the targeted study entry population of subjects with congenital adrenal hyperplasia when disease treatment is not optimum. In general, if events as listed in Appendix 3 occur and are considered serious, they will not be reported to regulatory authorities in an expedited safety report since causality will likely be due to the underlying medical condition, rather than to study drug. During the course of the trial, if aggregate analyses indicate that the events are occurring more frequently than anticipated, the sponsor will notify regulatory authorities expeditiously as appropriate.

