### *12.6 Assessment of Adverse Event Expectedness*

An AE is considered “unexpected” if it is not listed in the Investigator Brochure or is not listed at the specificity or severity that has been observed. “Unexpected,” as used in this definition, also refers to AEs that are mentioned in the Investigator Brochure as occurring with a class of drugs or as anticipated from the pharmacological properties of the drug, but are not specifically mentioned as occurring with the particular drug under investigation.

The concept of expectedness does not refer to what may occur in the course of the treated disease such as in the case of disease progression and/or lack of drug effect.

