#### **12.10.1 Standards for Expedited Reporting**

For each SAE/SUSAR, the investigator and sponsor (or designee) will independently assess whether there is a reasonable possibility that the event may have been caused by the study drug (“drug-related”). If the SAE is assessed to be both drug-related and unexpected, the sponsor or designee will report it to the appropriate regulatory authorities and notify investigators as required by applicable local regulations. The sponsor or designee will report SAEs to the US FDA as required by 21 CFR 312.32, and EU Competent Authorities as per EU requirements.

SUSARs are required to be reported within 7 calendar days for life threatening events and those resulting in death, or 15 calendar days for all others. These timeframes begin with the first notification of the SUSAR to the sponsor/designee.

All events qualifying as SAEs and SUSARs will be reported by the Pharmacovigilance Contract Research Organisation (CRO), as necessary, to Regulatory Authorities and ethics committees/IRB (the latter may be through the local investigator, as required by local regulations).

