## Appendix 3 - Expected Adverse Events

The active ingredient of Chronocort® is hydrocortisone. The safety profile of hydrocortisone is well characterised in humans and there is extensive clinical experience with the use of hydrocortisone in subjects with CAH. The excipients used in the Chronocort® formulation are also well-characterised and approved for use in humans at the proposed levels. The risks of Chronocort® are, therefore, expected to be no greater than the risks of an equivalent dose of cortisol.

For US NIH clinical centre only (new text in bold): The active ingredient of Chronocort® is hydrocortisone. The safety profile of hydrocortisone is well characterized in humans and there is extensive clinical experience with the use of hydrocortisone in subjects with CAH. The excipients used in the Chronocort® formulation are also well-characterized and approved for use in humans at the proposed levels. The risks of Chronocort® are, therefore, expected to be no greater than the risks of an equivalent dose of cortisol. **However, until the safety, efficacy and tolerability of this formulation in the treatment of individuals with CAH has been proven, the risk is considered to be greater than minimal risk with the prospect of direct benefit in individual subjects.**

The Summary of Product Characteristics (SmPC) of hydrocortisone is used as the reference for expected AEs (<http://www.medicines.org.uk/emc/medicine/27652>). However, some of the data in the hydrocortisone SmPC clearly relates to anti-inflammatory immunosuppressive doses of glucocorticoid, which will not be used in this study of Chronocort®. Should such immunosuppressive events be observed they would be unexpected so are not included.

The following is reproduced from section 4.8 of the hydrocortisone SmPC:

The incidence of predictable undesirable effects, including hypothalamic-pituitary-adrenal suppression correlates with the relative potency of the drug, dosage, timing of administration and the duration of treatment. The following side effects may be associated with the long-term systemic use of corticosteroids:

*Gastrointestinal:*

Dyspepsia, peptic ulceration with perforation and haemorrhage, abnormal distension, oesophageal ulceration, candidiasis, acute pancreatitis.

*Musculoskeletal:*

Proximal myopathy, osteoporosis, vertebral and long bone fractures, avascular osteonecrosis, tendon rupture.

*Fluid and electrolyte disturbance:*

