Sodium and water retention, hypertension, potassium loss, hypokalaemic alkalosis.

*Dermatological:*

Impaired healing, skin atrophy, bruising, striae, acne, telangiectasia.

*Endocrine/metabolic:*

Suppression of the hypothalamo-pituitary-adrenal axis, growth suppression in infancy, childhood and adolescence, menstrual irregularity and amenorrhoea. Cushingoid facies, hirsutism, weight gain, impaired carbohydrate tolerance with increased requirement for antidiabetic therapy, negative protein and calcium balance, and increased appetite.

*Neuropsychiatric:*

Euphoria, psychological dependence, depression, insomnia and aggravation of schizophrenia. Increased intracranial pressure with papilloedema in children (pseudotumour cerebri), usually after treatment withdrawal. Aggravation of epilepsy.

*Ophthalmic:*

Increased intra-ocular pressure, glaucoma, papilloedema, posterior subcapsular cataracts, corneal or scleral thinning, exacerbation of ophthalmic viral or fungal diseases.

*Cardiovascular:*

Myocardial rupture following recent myocardial infarction.

*General:*

Hypersensitivity, including anaphylaxis has been reported. Nausea, malaise, leucocytosis, thromboembolism.

*Withdrawal symptoms:*

Too rapid a reduction of corticosteroid dosage following prolonged treatment can lead to acute renal insufficiency, hypotension and death. A withdrawal syndrome may also occur including fever, myalgia, arthralgia, rhinitis, conjunctivitis, painful itchy skin modules and weight loss.

A wide range of psychiatric reactions including affective disorders (such as irritable, euphoric, depressed and labile mood, and suicidal thoughts), psychotic reactions (including mania, delusions, hallucinations, and aggravation of schizophrenia), behavioural disturbances, irritability, anxiety, sleep disturbances, and cognitive dysfunction including confusion and amnesia have been reported. Reactions are common and may occur in both adults and children. In adults, the frequency of severe reactions has been estimated to be 5-6%. Psychological effects have been reported on withdrawal of corticosteroids; the frequency is unknown.

In addition, 3 out of 16 subjects in a phase 2 study of Chronocort® had symptoms of carpal tunnel syndrome (median nerve compression), which may be related to fluid retention secondary to Chronocort® treatment.

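### Section 12.5 generally keeps serious Appendix 3 events out of expedited reports as disease events, but Appendix 3 lists drug side effects, so serious, unexpected suspected reactions could fail to be expedited

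*Protocol*

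**What the plan says.** Protocol Section 12.5 introduces the appendix this way: "Appendix 3 provides a comprehensive list of events that are anticipated to occur in the targeted study entry population", meaning subjects whose CAH is not optimally treated. It then says that when such events are serious, in general "they will not be reported to regulatory authorities in an expedited safety report", and gives the reason: "since causality will likely be due to the underlying medical condition, rather than to study drug". If aggregate analysis shows the events occurring more often than anticipated, the sponsor will notify regulators.

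Appendix 3 is titled as a list of expected adverse events and takes the hydrocortisone SmPC as its reference. Its main content is announced by "The following is reproduced from section 4.8 of the hydrocortisone SmPC" and "The following side effects may be associated with the long-term systemic use of corticosteroids". It closes with carpal tunnel syndrome seen in the phase 2 study, "which may be related to fluid retention secondary to Chronocort® treatment".

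The other reporting sections set different tests:

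- **12.6** makes an event unexpected if it is absent from the Investigator Brochure or "is not listed at the specificity or severity that has been observed". An event mentioned there only as an effect of the drug class also counts as unexpected.
- **12.10** requires expedited reporting of adverse drug reactions that are serious and unexpected.
- **12.10.1** has the investigator and the sponsor each judge, for every case, "whether there is a reasonable possibility that the event may have been caused by the study drug". Events judged related and unexpected go to regulators. SUSARs are due within 7 days if fatal or life-threatening and within 15 days otherwise.

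**The concern.** Section 12.5 treats Appendix 3 as a catalogue of what poorly controlled CAH does to patients and presumes a disease cause on that basis. The appendix is a catalogue of what corticosteroids do to patients. A rule that sets aside drug causality has therefore been attached to the list of effects most plausibly caused by the drug.

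What is at stake is expedited reporting to regulators. A safety group applying 12.5 could hold back a case that 12.10.1 requires to be sent, because its preferred term appears in Appendix 3. No endpoint, analysis set or estimate is affected, and SAP Section 11.2 still summarises SAEs by causality.

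**Working it through.** No arithmetic applies. The check sets the sections side by side.

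**1. What kind of list is Appendix 3?** The content comes from the side-effect section of a drug label, and the one added item is a suspected Chronocort effect. The appendix also explains that immunosuppressive events are left out because, at the doses used here, they would be unexpected. That is the logic of a drug-expectedness list. Adrenal crisis, which Section 12.9 gives among the events likely in CAH, is not an Appendix 3 term. Section 12.6 adds that expectedness does not concern the course of the treated disease. The description in 12.5 does not match the list.

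**2. Does a broader reading of suboptimal treatment rescue the reason?** Suppose it covers over-treatment. Corticosteroid side effects would then fit the description. But over-treatment effects come from the glucocorticoid, and 12.5 says that both Chronocort and the comparator glucocorticoids are IMPs. They remain suspected IMP reactions, and the disease-not-drug reason still fails.

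**3. Where do the rules give different answers?** Take a serious event whose term is in Appendix 3:

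| Case-level judgement | 12.6, 12.10 and 12.10.1 | 12.5 | Result |
|---|---|---|---|
| Not related to an IMP | Not expedited | Not expedited | Agree |
| Related, expected under 12.6 | Not expedited | Not expedited | Agree, but 12.5 gives a wrong reason |
| Related, unexpected under 12.6 | Expedited | In general, not expedited | **Conflict** |

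The conflict is confined to the third row. An event falls there if it is more severe or more specific than listed, or if the brochure mentions it only as a class effect. Section 12.5 makes no exception for severity, specificity or a case-level finding of relatedness.

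**4. An illustration.** Section 5 describes the phase 2 carpal tunnel cases as mild. Suppose a subject is admitted to hospital with carpal tunnel syndrome and the investigator judges it related. If the brochure lists only the milder presentation, 12.6 makes the case unexpected and 12.10.1 sends it to regulators. Section 12.5 would presume a disease cause, although Appendix 3 suggests Chronocort. Whether the case is in fact unexpected depends on the brochure wording.

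**5. What still operates if 12.5 is followed?** Section 12.9 sends treatment-period SAEs to the sponsor within 24 hours with no exception for Appendix 3 terms, and provides for periodic reports. Section 12.13 provides DSMB review of safety data. Section 12.10.2 separately lists a rise in the rate of an expected serious reaction as a ground for considering an expedited report.

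**6. Size.** The third row cannot be counted. Section 12.6 defines expectedness by the Investigator Brochure, which is not among the documents. The amendment history (Appendix 10, version 2.0) links Appendix 3 to the brochure's reference safety information but does not reproduce it.

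**The case against.** The strongest case on the other side is that 12.5 makes a loose general statement and that 12.10, 12.10.1 and 12.11 are the operative rules. The sentence is qualified as a generality. The paragraph before it says that an event judged by either the investigator or the sponsor to have a reasonable suspected link to an IMP is an adverse drug reaction, and 12.10 and 12.11 then require serious unexpected ones to be expedited. Read as a whole, the protocol may already give the right answer. This stands in part: it means such cases could be held back, not that they would be. It does not remove the conflict, because the qualifier gives no criterion for an exception and nothing says which section prevails.

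A reader might also infer more than the documents support:

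- **That all serious Appendix 3 events are wrongly withheld**, including perforated peptic ulcer, acute pancreatitis, thromboembolism and anaphylaxis. These are named in a list of expected events. As listed, they would probably not be expedited under 12.10 either.
- **That these reactions would go unreported altogether.** Only the expedited route to regulators is in question.
- **That no frequency safeguard remains.** The trigger in 12.5 has no anticipated rates beside it or in Appendix 3, but the trigger in 12.10.2 does not depend on a disease list.
- **That the appendix has nothing to do with CAH.** Some terms, such as striae, hirsutism and amenorrhoea, are also signs of over- or under-treatment in Section 5. That overlap is too small to justify a disease presumption for the whole list.

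**Conclusion.** The point holds within limits. The reason given in 12.5 is wrong for the list it cites, and its exemption contradicts 12.6, 12.10 and 12.10.1 for serious suspected reactions that share an Appendix 3 term but are unexpected under 12.6. If 12.5 were followed, those cases could miss the 7- or 15-day report.

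The number of such cases is unknown and may be small. The conclusion assumes that someone could apply 12.5 as written, without reading the later sections as overriding it, and that the brochure leaves some events in the unexpected category. The documents do not support describing 12.5 as an absolute ban on expediting, or taking the whole of Appendix 3 as the measure of what is at risk. The change is still worth making, because the contradiction sits in a safety-reporting rule and is easily removed.

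**What to change.** In Section 12.5, delete the presumption of disease causality and the exemption tied to Appendix 3. Replace them with a statement that 12.6 and 12.10.1 decide expedited reporting, through causality judged case by case and listedness at the observed specificity and severity. Appendix 3 can stay as the list of expected drug effects.

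If the sponsor wants to exempt events of the disease itself, add a separate list of CAH events with an anticipated rate for each, so that the aggregate comparison in 12.5 has something to be measured against.

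The cost is one protocol paragraph, or a paragraph and a short list if the exemption is kept, and possibly a few more expedited reports. The statistical analysis does not change.
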